2. STUDY OBJECTIVES

The main objective of this study was to evaluate the efficacy of Ivermectin 1% topical cream (IVM) associated with Doxycycline (Doxy) 40 mg Modified release (MR) capsules versus Ivermectine 1% topical cream associated with Placebo in the treatment of severe rosacea. The Safety and Patient Reported Outcomes (PRO) were also be evaluated.

3. INVESTIGATIONAL PLAN

3.1 OVERALL STUDY DESIGN

This study was to be conducted as a multi-center, randomized, investigator-blind, vehicle-controlled and parallel-group comparison trial, involving subjects of any gender or race, aged 18 years or older, with severe rosacea characterized by persistent diffuse facial erythema and inflammatory lesions (papules and pustules), and meeting specific inclusion/exclusion criteria.

A total of 270 subjects (135 in each group) were to be enrolled at approximately 50 sites in the United States of America, Canada and Europe (Germany, Czech Republic, Hungary and Poland). Subjects were to be enrolled at baseline and, depending on randomization scheme, were to be treated for 12 weeks as follows:

IVM/Doxy:

- Ivermectin 1% cream: one small pea size amount per facial region (forehead, chin, nose, and each cheek) once a day in the evening for 12 weeks.
- Doxycycline 40 mg MR (30 mg Immediate Release & 10 mg Delayed Release beads): 1 capsule once-daily in the morning on an empty stomach for 12 weeks.

IVM/Placebo:

- Ivermectin 1% cream: one small pea size amount per facial region (forehead, chin, nose, and each cheek) once a day in the evening for 12 weeks.
- CD2475-101 placebo: 1 capsule once-daily in the morning on an empty stomach for 12 weeks.

There were up to 5 study visits: screening/baseline, week 4, week 8 and week 12.

3.2 SAMPLE SIZE CONSIDERATION

3.2.1 Historical data and assumptions

No previous study exists associating Ivermectin 1% cream and Doxycycline MR. Therefore, this sample size was calculated using the results of previous studies on subjects treated with Ivermectin 1% cream alone and Doxycycline MR alone.

With Ivermectin 1% cream alone, for % change from baseline in inflammatory lesion counts at week 12, results showed a standard deviation (SD) between 25.4% to 39.9% with a mean around 35%.

With Doxycycline MR alone, results showed a minimum difference of 26% at Week 12 versus Placebo.

Using this historical data, we assumed that the difference between the association (Ivermectin + Doxy) and (Ivermectin + Placebo) was at least of 15% with a SD of 35%.

3.2.2 Sample size calculation

With the assumptions mentioned above, a total of 114 evaluable subjects per group were to be required to demonstrate at least 15% difference at Week 12, with 90% power.

To allow a 15% rate of subjects excluded from analysis (drop out, lost to follow-up, etc.) at Week 12, 135 subjects per group (270 in total) were to be enrolled.

4. ANALYZED VARIABLES

4.1 EFFICACY VARIABLES

4.1.1 Primary efficacy variable

➤ Percent change from Baseline in inflammatory lesion (IL) count at Week 12: The evaluator performed inflammatory lesion count on facial papules and pustules of rosacea.

4.1.2 Secondary efficacy variables

- ▶ Percent change from Baseline in IL count at each intermediate visit: (week 4 and week 8).
- Percent of subject clear inflammatory lesions at each post-baseline visit: % of subject with 100% reduction of IL.
- ➤ Clinical Erythema Assessment (CEA) at each visit: % of subject across score. The evaluator assessed the subject's diffuse persistent facial erythema of rosacea by performing a static ("snap shot") evaluation of erythema severity at a social distance of approximately 50 cm using CEA, at each visit.

Grade	Score	Description
Clear	0	Clear skin with no signs of erythema
Almost Clear	1	Almost clear; slight redness
Mild	2	Mild erythema; definite redness
Moderate	3	Moderate erythema; marked redness
Severe	4	Severe erythema; fiery redness

Investigator's Global Assessment (IGA) at each post-baseline visit: % of subject across score. The evaluator assessed the subject's rosacea at each visit by performing a static ("snap-shot") evaluation at a social distance of approximately 50 cm, using IGA score. No reference to previous visits was to be made.

Grade	Score	Clinical Description	
Clear	0	No inflammatory lesions present, no erythema	
Almost Clear	1	ery few small papules/pustules, very mild erythema present	
Mild	2	Few small papules/pustules, mild erythema,	
Moderate	3	Several small or large papules/pustules, moderate erythema,	
Severe	4	Numerous small and/or large papules/pustules, severe erythema,	

> Stinging/Burning at each post-baseline visit: % of subject across score. The evaluator recorded the severity of subject's facial stinging/burning sensation (a prickling pain sensation) during the last 24h at each visit.

None	0	No stinging/burning		
Mild	1	ht warm, tingling/stinging sensation; not really bothersome		
Moderate	2	Definite warm, tingling/stinging sensation that is somewhat bothersome		
Severe	3	Hot, tingling/stinging sensation that has caused definite discomfort		

> Subject's Global Improvement in Rosacea at week 12/early termination visit: % of subject across score. The subject evaluated his/her improvement in rosacea at last visit compared with his/her rosacea condition before the study

Complete Improvement	0	All signs and symptoms of disease have resolved (100% improvement from Baseline)
Excellent Improvement	1	Nearly all signs and symptoms cleared (90% improvement from Baseline)
Very good Improvement	2	Majority of the signs and symptoms have resolved (about 75% improvement from Baseline)
Good Improvement	3	Significant improvement, but many signs and symptoms remain (about 50% improvement from Baseline)
Minimal Improvement	4	Slight overall improvement, but many signs and symptoms remain (about 25% improvement from Baseline)
No Change	5	Overall severity similar from Baseline
Worse	6	Worse than Baseline

4.1.3 Exploratory efficacy variables

➤ Global assessment of ocular signs and symptoms at each post-baseline visit: % of subject across score. The evaluator recorded the severity of the ocular signs and symptoms after discussion with the subject.

Grade	Score	Clinical Description
None	0	No ocular sign/symptom
Mild	1	Mild blepharitis with lid margin telangiectasia
Mild-Moderate	2	Blepharoconjunctivitis
Moderate-Severe	3	Blepharo-keratoconjunctivitis
Severe	4	Sclerokeratitis, anterior uveitis

- ➤ Percent change from baseline (medical history) in terms of flushing count per week: At baseline the investigator recorded in medical history the frequency of flushing as reported by subject for the previous week before baseline visit. During the study, the number of weekly flushing was reported in the eCRF by the investigator or designee based on the flushing episodes recorded daily by the subject in the diary.
- ➤ Change from baseline (medical history) in mean score severity per week: At baseline the investigator recorded in medical history the average severity of flushing by grading as mild, moderate or severe. (severity from the previous week before baseline visit). During the study, the average severity was reported in the eCRF by the investigator or designee based on the severity recorded daily by the subject in the diary.
- ➤ Change from baseline in Facial redness colorimetric measurements (CEI) at each post-baseline visit: In selected investigational sites, the investigator assessed the colorimetry using a Chromameter that converts colors perceived by the human eye into a digital code composed of the following parameters: L*: for clarity (from dark to light), a*: for the green-to-red component, b*: for the blue-to-yellow component.

When evaluating an erythema, the a* parameter is of highest importance. The decrease in luminance L* can also be considered useful because it reflects the darkest character of an erythema. The CEI (Colormetric Erythema Index) is the reflection of these two parameters. It is calculated on the zone treated with the tested product and the blank formulation zone according to the following formula: $CEI = (\Delta L^{*2} + \Delta a^{*2})1/2$

 ΔL^* : variation in the skin luminosity under the effect of the erythema

 Δa^* : variation in the skin color on the green-to-red axis under the effect of the erythema.

4.2 PATIENT-REPORTED OUTCOMES VARIABLES

> Dermatology Life Quality Index (DLQI) at week12/early termination: % of subject across Total score at baseline and last visit; and the % change from baseline.

Grade	Description
0-1	No effect at all on patient's life
2-5	Small effect on patient's life
6-10	Moderate effect on patient's life
11-20	Very large effect on patient's life
21-30	Extremely large effect on patient's life

- ➤ EQ-5D questionnaire at week12/early termination: % of subjects across score of questions at baseline and last visit.
- > Work Productivity and Activity Impairment Questionnaire at week 12/early termination: General Health (WPAI: GH) modified for Rosacea. % of subjects across score of questions at baseline and last visit.
- > Subject's satisfaction questionnaire at week12/early termination: % of subjects across score of questions at last visit.

4.3 SAFETY VARIABLES

➤ Adverse events: Incidence of adverse events - All clinical medical events, whether observed by the investigator or reported by the subject and whether or not thought to be study product -related were to be considered adverse events.

5. POPULATIONS ANALYZED

The definition of the populations and the pooling center will be finalized after a blind data review meeting, during which the distribution of subjects per site will be reviewed.

5.1 INTENT TO TREAT POPULATION (ITT)

This population consists of the entire population enrolled and randomized (i.e., assigned a kit number). The ITT population will be used for all variables except the safety variables.

5.2 PER PROTOCOL POPULATION (PP)

The PP Population is defined as comprising the ITT subjects who have no major protocol deviations that will be refined during a blind review. The primary efficacy endpoint will be analysed based on this population.

5.3 SAFETY POPULATION (ALL SUBJECT TREATED (APT))

This population consists of the ITT population, after exclusion of subjects who never used the treatment with certainty based on monitoring report. The APT population will be only used for the safety variables (AEs)

5.4 MISSING VALUES

In order to evaluate the effect of major deviations or of data exclusions, the last observation carried forward (LOCF) method will be used to impute missing values for inflammatory lesion count and IGA. If no post-baseline data are available, baseline will be carried forward. Thus, the number of subjects will not vary at each visit. The other missing values will not be replaced (observed data).

5.5 POOLING OF CENTERS

In case of too small sites or in case of severe unbalance between the size of sites, some sites may be combined, e.g. per geographical area, to form analysis-center for purpose of stratification of the statistical analyses.

6. STATISTICAL METHODS AND DATA CONSIDERATIONS

SAS version 9.3 will be used for all analyses. All tests will be two-sided and significance will be declared at a 0.05 level.

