The primary efficacy criterion will be analyzed by using the Cochran-Mantel-Haenszel (CMH) statistic, stratified by center (or analysis-center) after ridit transformation with the row mean difference statistics, testing the hypothesis of equality. The p-value will have to be inferior to 0.05 at Week 12, on ITT/LOCF population. PP analysis will be also performed to assess the robustness of the results obtained on ITT/LOCF population.

The other variables will be analyzed similarly as primary analysis on appropriate population. Each test will be two-sided, at the 0.050 significance level.

The subject characteristics (previous medication, concomitant medication, demographics, baseline characteristics...), lesion counts and adverse events, will be summarized by descriptive statistics (usual statistics and frequency distribution)

Protocol N° RD.03.SPR.113322

version Final dated 10-FEB-2017

Page 27 of 106 CONFIDENTIAL

Protocol N° RD.03.SPR.113322

version Final dated 10-FEB-2017

Page 28 of 106 CONFIDENTIAL

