6.3 EFFICACY ANALYSES

6.3.1 Primary efficacy analyses

The primary objective of this study was to demonstrate the superiority of the IVM/Doxy compared to IVM/Placebo, in terms of percent change from baseline in inflammatory lesion count at week 12.

The primary efficacy endpoint will be analyzed by using the Cochran-Mantel-Haenszel (CMH, FREQ procedure from SAS®) statistic, stratified by center (or analysis-center) after ridit transformation with the row mean difference statistics, testing the hypothesis of equality on ITT/LOCF population. PP analysis will also be performed to assess the robustness of the results obtained on ITT/LOCF population. The p-values will have to be inferior to 0.05 at week 12.

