6.3.2 Secondary and other efficacy analyses

The variables will be analyzed similarly as primary analyses on ITT/LOCF population at each post-baseline evaluation time on appropriate population.

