6.4 PATIENT-REPORTED OUTCOMES ANALYSES

DLQI, EQ-5D-5L, WPAI-GH and subject satisfaction questionnaires will be statistically analyzed similarly as primary analyses on ITT population at each post-baseline evaluation time.

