14.2.2. Secondary efficacy analyses

14.2.2.1. Inflammatory lesions

Table 16. Inflammatory lesions: % change from baseline at other post-baseline visit (ITT/LOCF)

	IVM + Doxycycline	IVM + Vehicle	p-value (1)
Week 4 (ITT/LOCF)			XXX
N			
Mean ±SD			
Median			
Min,Max			
Week 8 (ITT/LOCF)			XXX

⁽¹⁾ p-value of CMH test based on ridit scores stratified by analysis-center.

Table 17. Inflammatory lesions: 100% reduction from baseline at each post-baseline visit (ITT/LOCF)

	IVM + Doxycycline	IVM + Vehicle	p-value (1)
Week 4 (ITT/LOCF)			XXX
N			
No (n,%)			
Yes(n,%)			
Week 8 (ITT/LOCF)			XXX
Week 12 (ITT/LOCF)			XXX

⁽¹⁾ p-value of CMH test based on ridit scores stratified by analysis-center.

Table 18. Inflammatory lesions: Count at each visit - Descriptive (ITT/LOCF)

	IVM + Doxycycline	IVM + Vehicle
Baseline		
N		
Mean ±SD		
Median		
Min,Max		
Week 12 (ITT/LOCF)		

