14.2.2.2. Clinician's Erythema Assessment

Table 19. Clinician's Erythema Assessment: Raw value at each visit (ITT/LOCF)

	IVM + Doxycycline	IVM + Vehicle	p-value (1)
Baseline			NA
Week 4 (ITT/LOCF) N 0: Clear n (%) 1: Almost clear n (%) 2: Mild n (%) 3: Moderate n (%) 4: Severe n (%) Mean ±SD Median Min,Max			XXX
Week 12 (ITT/LOCF)			XXX

⁽¹⁾ p-value by CMH test based on ridit scores stratified by analysis-center.

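### The plan declares significance at two-sided 0.05 for every test, with no gate on the primary, no order among the secondary tests and no nominal label for the rest

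*SAP*

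**What the plan says.** The decision rule is in SAP section 6: "All tests will be two-sided and significance will be declared at a 0.05 level". The protocol synopsis has its counterpart, placed directly after the sentence on the non-primary variables: "Each test will be two-sided, at the 0.050 significance level".

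The primary endpoint is one variable at one time: percent change in inflammatory lesion count at Week 12, ITT with LOCF, tested by a centre-stratified CMH test on ridit scores. SAP 6.3.1 attaches a success condition to it: "The p-values will have to be inferior to 0.05 at week 12". A per-protocol analysis is added for robustness.

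SAP 6.3.2 then extends the same test downwards: "The variables will be analyzed similarly as primary analyses on ITT/LOCF population at each post-baseline evaluation time on appropriate population". SAP 6.4 does so for the four questionnaires, which are to be "statistically analyzed similarly as primary analyses on ITT population at each post-baseline evaluation time". The shells for Tables 16, 17, 19 to 24, 26, 28, 31, 33 and 35 to 39 carry a p-value column.

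Neither document states a testing order, a condition that the primary must succeed first, a multiplicity adjustment, or that non-primary p-values are nominal or descriptive. SAP section 7, on changes from the protocol analysis, lists only the added endpoint of complete lesion clearance.

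**The concern.** Running many secondary and exploratory tests without adjustment is ordinary practice when the p-values are offered as nominal. This plan goes further: it says that significance will be declared, and it says so for all tests.

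Two consequences follow. First, if the Week 12 lesion test fails, nothing in the plan stops the report from declaring a significant benefit on IGA, erythema, clearance or a questionnaire. Second, if the primary succeeds, any secondary endpoint and visit that falls below 0.05 may be called significant, with no control over the chance that at least one such statement is false.

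Claims of this kind are foreseeable. Protocol 3.2 names time to onset and patient satisfaction among the benefits to be evaluated, and Protocol 2.3 raises the possibility of a faster response. The Week 4 and Week 8 tests and the questionnaires are where such claims would be sought.

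**Working it through.** **The plan's own figures.** The documents state no number of tests and no familywise error rate. The only error-rate calculation is the sample size for the primary (Protocol 9.2, SAP 3.2): difference 15, SD 35, power 90%. The section gives no alpha, so 0.05 two-sided is taken from SAP section 6.

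n per group = 2 × [35 × (1.960 + 1.282) / 15]² = 114.4, against a stated 114. Then 114 / 0.85 = 134.1, hence 135 enrolled. The sample size is therefore consistent with the full 0.05 being spent on one primary test.

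**Count of non-primary tests.** Several shells are abbreviated. Visit-based tables are read as Weeks 4, 8 and 12, as SAP 6.3.2 requires. Satisfaction items are counted from Protocol Attachment 4.

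| SAP tier | Tables and tests | Total |
|---|---|---|
| Secondary | T16: 2; T17: 3; T19: 3; T20: 3; T21: 3; T22: 1 | 15 |
| Exploratory | T23: 3; T24: 12; T26: 12; T28: 3 | 30 |
| Questionnaires | T31: 2; T33: 6; T35: 6; T36: 12; T37: 10; T38: 4; T39: 4 | 44 |
| All | 15 + 30 + 44 | 89 |

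Tables 24 and 26 (flushing) print only the Week 1 and Week 12 rows. Protocol 9.1.1.2 describes flushing per week over 12 weeks, which supports 12 tests each. Counting only the printed rows removes 20 tests: 89 − 20 = 69.

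**Expected false positives if there is no effect anywhere.** The mean is 0.05 × number of tests. It needs true nulls and tests at nominal size, but not independence.

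- 15 secondary tests: 15 × 0.05 = 0.75
- 69 tests: 69 × 0.05 = 3.45
- 89 tests: 89 × 0.05 = 4.45

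**Chance of at least one false positive among the 15 secondary tests.** If independent, it is 1 − 0.95^15 = 0.537 in either direction, and 1 − 0.975^15 = 0.316 in favour of the combination.

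The tests are not independent, since many are the same scale at successive visits. The documents give no correlations, so equal correlation ρ between normal test statistics is assumed. Conditional on a shared standard normal factor f, each statistic is non-significant with probability

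q(f) = Φ[(1.96 − √ρ f)/√(1−ρ)] − Φ[(−1.96 − √ρ f)/√(1−ρ)],

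and the chance of at least one false positive is 1 − ∫ φ(f) q(f)^15 df. For the direction favouring the combination, only the first term of q is kept.

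| Assumed ρ | At least one, either direction | At least one favouring the combination |
|---|---|---|
| 0 | 54% | 32% |
| 0.3 | 46% | 23% |
| 0.5 | 36% | 18% |
| 0.7 | 26% | 13% |

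**Spread over all 89 tests.** Under the same model at ρ = 0.3, 0.5 and 0.7, the mean stays near 4.45, but the median count is 3, 2 and 0, and the chance of at least one is about 93%, 75% and 48%.

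**The case against.** The strongest reply is that the plan already separates what it sets out to prove from the rest. There is one primary variable, followed by secondary, exploratory and patient-reported tiers. Only the primary has a superiority objective and a required p-value. Seven shells (Tables 18, 25, 27, 29, 30, 32 and 34) are marked descriptive and carry no p-value, baseline comparisons are marked not applicable, and adverse events are only summarised. That stands. A reader might infer that nothing in the plan distinguishes claims from description; the documents do not support that. The gap is narrower: the tiers exist, but the rule for declaring significance ignores them.

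A second reply is that the large count comes mostly from the lower tiers: 74 of the 89 tests are exploratory or questionnaire items, and 18 concern the cleanser and moisturizer. The count also rests on how abbreviated shells are read. Both points stand, which is why the size of the problem is best judged on the 15 secondary tests, with 69 to 89 given as a range.

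A third reply is that correlation makes the independent-case figures too high. This also stands. The 54% is the largest of the values shown, and the lower rows of the table belong beside it.

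A reader might also bring in the visible difference in capsule marking (Protocol 6.5.1) as making the subject-reported tests less reliable. That is a question of bias. Ordering or relabelling tests does not correct it, and it forms no part of this point.

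**Conclusion.** The concern holds for secondary, exploratory and questionnaire claims. The plan contains an explicit rule that permits significance to be declared on any of them, whether or not the primary succeeds. For the 15 secondary tests under no effect, 0.75 false positives are expected. The chance of at least one lies between about 26% and 54% over assumed correlations from 0.7 down to 0, and between 13% and 32% in favour of the combination. Across all non-primary tests the mean is about 3.5 to 4.5.

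These figures assume that every null hypothesis is true, that each test has its nominal size (sparse questionnaire items may depart from it) and, for the probabilities, equal correlation between tests.

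Two stronger readings should be resisted. One is that the primary conclusion is compromised: it is a single test at one visit, and its 5% error is untouched. The other is that several false findings should be counted on in this trial. The 3.5 to 4.5 is an average, and with strongly correlated tests the usual result could be none, with occasional large clusters.

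**What to change.** In SAP section 6, limit the declaration of significance at 0.05 to the primary Week 12 ITT/LOCF test, and state that all other p-values are nominal and will not be described as significant. Every planned analysis and table can stay.

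If the sponsor wants secondary claims, add a short list of endpoints and visits in an order that it fixes before unblinding. Test each at two-sided 0.05, and only while the primary and every previous step are significant. Which endpoints enter, and in what order, is the sponsor's choice.

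Record the change in SAP section 7 as a departure from the per-test rule in the protocol synopsis. If the SAP is already final, Protocol 9.1 requires the change to be documented in the clinical trial report.

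The cost is small: no extra subjects, no change to the primary test or its power, and no new analyses. The real price is that secondary endpoints outside the sequence, or after its first non-significant step, cannot be claimed as significant.

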6.1 DATA PRESENTATION

All continuous data will be summarized at each visit using usual statistics: number of values, mean, median, standard deviation, minimum and maximum, and by frequency distribution (n, %) for qualitative data. For ordinal data, both frequency distribution and usual statistics will be presented. All tables will be presented by parallel group and by visit (when applicable).

The adverse events will be descriptively summarized (n, %). All summaries are based on the safety population (APT). The adverse events will be descriptively summarized (n, %) by relationship to study treatments within System Organ Class (SOC) and preferred term (MedDRA). Subjects will be descriptively summarized (n, %) by intensity (*i.e.* mild, moderate and severe) of adverse event, SOC and preferred term. Deaths and serious adverse events will be reported as well as withdrawals due to adverse events. A subject will be counted once per System Organ Class (SOC) and once per preferred term even if more than one occurrence of an event was reported within a SOC or preferred term. In the summary by categories of intensity, the adverse event with the highest intensity will be used. The subject will be counted once per SOC (highest intensity whatever the AE within the SOC) and once per preferred term (highest intensity whatever the AE within the preferred term).

